9.6 Analyses

9.6.1 Comparison of CIN2+ between Arms A and B

For the primary analysis, time-to-event methods will be used to estimate the cumulative rate of the primary endpoint (from week 26 to week 130 after study entry) to account for lost to follow-up. The protocol team plans to use the Turnbull estimation for the proportions of participants without CIN2+ diagnosis by the end of the study, stratified by the study stratification factors [43]. The generalized Greenwood's formula for the standard error will be used for the variance and inverse variance method to account for strata [44]. The proportions in Arms A and B will be compared using asymptotic normal distributions. A one-sided 95% upper confidence bound on the difference (Arm B proportion minus Arm A proportion) between these proportions will also be provided. A stratified log-rank test will be conducted as a secondary analysis to compare the time to development of CIN2+ between Arms A and B. The primary analysis will be conducted as intent-to-treat on all participants randomized to the study Arms A and B. In other words, participants will be included in the analyses even if cryotherapy is not performed in Arm A and participants do not adhere to the strategy in Arm B. Per-protocol analysis will also be performed on only the participants who adhere to the specified procedures in Arms A and B, as secondary analysis. Participants without complete biopsy data will be censored at their last visit with a biopsy result (i.e., weeks 26, 78, 130).

Participants in Arm B may have biopsy done prior to week 26 based on the evaluation of baseline abnormal cervical cytology, whereas participants in Arm A will not have biopsies until week 26. Participants in Arm B diagnosed prior to their week 26 visit with CIN2+ that is cleared according to the biopsy at their week 26 will not be considered failures for the primary endpoint analysis. They are counted as meeting the primary endpoint only if CIN2+ is found at week 26 or later. Unplanned biopsies in Arm A that occur prior to the week 26 visit will not be considered for the primary endpoint.

The pathologic classification for the primary endpoint will be the determination by the local review at a DAIDS-assessed laboratory. Central review will be done for quality assurance.

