### **3 Statistical Considerations**

Unless otherwise indicated, analysis will use data from all subjects who enrolled successfully to A5282 arms A and B.

For categorical measures, number of subjects and percent will be provided. For continuous measures, median, lower and upper quartiles, minimum and maximum will be provided. In data listings, participants will be identified by an anonymous patient identifier generated at the statistical center. Dates will not be shown, but will be converted to time (e.g. weeks) since randomization.

Time to CIN2+ will be computed as the number of weeks between randomization and the week 26 to week 130 biopsy week when CIN2+ was first detected. For those who did not develop CIN2+, event time will be censored at the latest among the following: time of last biopsy or last colposcopy or last pap smear. The cumulative rate of CIN2+ will be estimated using Kaplan-Meier methods. A one-sided 95% upper confidence bound on Arm B minus Arm A cumulative rates accounting for baseline ART use (i.e. [using inverse variance as weights,] weighted estimate of treatment difference across baseline ART use) will be provided.

The per-protocol secondary analysis of the primary endpoint will only include:

- a. Arm A participants who had week 0 cryotherapy, and
- b. Arm B participants with: 1) baseline NILM cytology, 2) baseline abnormal cytology (ASCUS or greater) with one or more cervical biopsies that show NILM or CIN1 as the most severe result, 3) baseline abnormal cytology (ASCUS or greater) who underwent cervical colposcopy with no lesions seen, or 4) women who had LEEP performed prior to week 16 after the week 0 CIN2+ on biopsy regardless of cytology result.

All programs that generate derived data will be validated. The calculations of time to CIN2+ and confidence interval for the primary endpoint (one-sided 95% upper confidence interval for arm B proportion minus arm A proportion) will be double-programmed.

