#### 4.1.5 Baseline Summaries

- Baseline demographics, sociodemographic and health variables: age, race/ethnicity, IV drug use history, ART use, CD4 count, nadir CD4 count, highest level of education complete, average annual household income, number of children
- Baseline sexual history: age of first vaginal sex, total number of vaginal sex partners
- Baseline cytology and Abbott hr-HPV results

**4.2 Primary Endpoint:** CIN2+ (CIN2, CIN3 or invasive cancer) by biopsy 26 weeks post randomization through 130 weeks post randomization, as determined by local review at a DAIDS-assessed laboratory

Note: LEEP outcome prior to week 16 will be considered baseline evaluation and will not be used as an endpoint.

Tables (ITT and per-protocol): cumulative rates of arm A and arm B subjects who developed CIN2+ from week 26 to week 130; one-sided 95% upper CI for arm B proportion minus arm A proportion.

SDAC validation: The calculation of time to CIN2+ and the one-sided 95% upper CI will be double-programmed.

In addition, (to evaluate design assumptions and precursory design assumptions,) the following will be reported:

- Arm A and Arm B: CIN2+ rate from week 26 to week 130
- Arm A and Arm B: week 0 invasive cancer
- Arm B: number (%) diagnosed with CIN2+ at baseline
- Arm B: number (%) with CIN2+ at baseline who were successfully treated before week 26. Note that we only have a limited number of participants with cervical (non-LEEP) biopsy results before week 26.
- number (%) of subjects with abnormal pap smear and CIN2+ at baseline
- number (%) of subjects with CIN2+ at baseline who were successfully treated before week 26.

**4.2.1 Secondary endpoint:** Time to CIN2+ diagnosis by biopsy, as determined by local review at a DAIDS-assessed laboratory

Figures (ITT and per-protocol): survival curves with p-value from stratified log-rank test comparing arms A and B.

Figure: For Arm A, survival curves with p-value from log-rank test comparing participants with and without hr-HPV at week 26 based on: (a) aHPV, and (b) Xpert

Figure: For Arm A, survival curves with p-value from log-rank test comparing participants with and without cervical cytologic abnormalities at week 26.

Figures (ITT): survival curves with p-value from stratified log-rank test comparing arms A and B.

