Figures (ITT): survival curves with p-value from stratified log-rank test comparing arms A and B for those with: (a) CIN2+ on histology at baseline, (b) CIN1 on histology at baseline, (c) NILM cytology result at baseline, (d) ASCUS/LSIL cytology result at baseline and (e) HSIL/ASC-H cytology result at baseline.

**4.2.2 Secondary endpoint:** CIN3+ (CIN3 or invasive cancer) by biopsy 26 weeks post randomization through 130 weeks post randomization, as determined by local review at a DAIDS-assessed laboratory.

NOTE: Time to CIN3+ will be computed as the number of weeks between randomization and the biopsy week when CIN3+ was detected. For those who did not develop CIN3+, event time will be censored at the latest among the following: time of last biopsy or last colposcopy or last pap smear.

Tables (ITT and per-protocol): cumulative rates of arm A and arm B subjects who developed CIN3+ from week 26 to week 130; two-sided 95% CI for arm B proportion minus arm A proportion.

Figures: survival curves with p-value from stratified log-rank test comparing arms A and B

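### The SAP's primary confidence limit is an upper bound on Arm B minus Arm A CIN2+ event rates, which is the side that cannot show superiority of cryotherapy

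*SAP*

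**What the plan says.** Protocol 9.6.1 works on the event-free scale. It plans "Turnbull estimation for the proportions of participants without CIN2+ diagnosis by the end of the study", then states "The proportions in Arms A and B will be compared using asymptotic normal distributions", and adds "A one-sided 95% upper confidence bound on the difference (Arm B proportion minus Arm A proportion) between these proportions will also be provided".

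SAP section 3 works on the event scale. It estimates the cumulative rate of CIN2+ by Kaplan-Meier, and the next sentence plans "A one-sided 95% upper confidence bound on Arm B minus Arm A cumulative rates accounting for baseline ART use". The estimate is weighted by inverse variance across baseline ART use. The validation sentence in the same section says that the "confidence interval for the primary endpoint (one-sided 95% upper confidence interval for arm B proportion minus arm A proportion) will be double-programmed".

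SAP 4.2 describes the primary table as cumulative rates of subjects "who developed CIN2+ from week 26 to week 130; one-sided 95% upper CI for arm B proportion minus arm A proportion". It then repeats that this one-sided upper limit will be double-programmed. It lists no test, p-value or lower limit.

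Two neighbouring items differ. SAP 4.2.1, a secondary endpoint, plans "survival curves with p-value from stratified log-rank test comparing arms A and B". The CIN3+ table in SAP 4.2.2 covers "subjects who developed CIN3+ from week 26 to week 130; two-sided 95% CI for arm B proportion minus arm A proportion".

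The hypothesis is the same in both documents (protocol 1.1, SAP 2.2): a lower probability of CIN2+ with immediate cryotherapy. Protocol 9.1 tests it one-sided for a reduction.

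**The concern.** The protocol is coherent. If cryotherapy works, fewer women in Arm B remain free of CIN2+, B minus A is negative, and an upper bound below 0 rules out no benefit at the one-sided 5% level.

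Moving to event rates reverses the sign. A benefit then makes B minus A positive, and the limit that must clear 0 is the lower one. The SAP made the move without reversing either the side of the limit or the subtraction. Its limit can cap the size of a benefit or, if it falls below 0, show harm. It cannot support the trial's hypothesis. Protocol 9.1 says that formal evidence of a result against cryotherapy is not needed.

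The primary table would therefore carry the uninformative limit, while the secondary CIN3+ table, with its two-sided interval, shows both. Double programming would not catch this, because two programmers following SAP 3 literally would agree on the same wrong-side limit. Correcting it after the data are seen could look like a post hoc choice.

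**Working it through.** **Inputs.** Arm B 20%, Arm A 6%, 111 per arm, one-sided 5%, 90% power (protocol 9.4); 140 per arm enrolled (protocol 9.4). The bounds below use complete binomial data with unpooled variance and z = 1.645. Censoring and the ART strata are ignored. They would change the width of the interval, not the side that is needed.

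**Step 1: reproduce the plan's sample size.** With d = 0.14 and mean rate 0.13, the uncorrected size is

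n₀ = [1.645·√(2·0.13·0.87) + 1.282·√(0.20·0.80 + 0.06·0.94)]² / 0.14² ≈ 97.

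With the continuity correction,

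n = (n₀/4)·[1 + √(1 + 4/(n₀·d))]² ≈ 111.

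This matches the protocol. The nine powers in protocol Table 2 also reproduce (90.06% for 20% versus 6%). The design is therefore one-sided in favour of Arm A.

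**Step 2: bounds at the design rates, 111 per arm.**

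SE = √[(0.20·0.80 + 0.06·0.94)/111] = 0.0442, so 1.645·SE = 0.0726.

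| Scale | B minus A | Limit | Value | Supports superiority? |
|---|---|---|---|---|
| CIN2+-free (protocol 9.6.1) | −0.14 | upper | −0.067 | Yes, below 0 |
| CIN2+ event (SAP 3, 4.2) | +0.14 | upper | +0.213 | No |
| CIN2+ event | +0.14 | lower | +0.067 | Yes, above 0 |

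The first and third rows are the same statement with the sign reversed. With 140 per arm (SE 0.0393) the event-scale limits are +0.205 (upper) and +0.075 (lower).

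**Step 3: the same limit with no effect.** At 20% in both arms, SE = √(2·0.20·0.80/111) = 0.0537, and the SAP's upper bound is 0 + 1.645·0.0537 = +0.088. The SAP's bound lies above 0 with probability over 0.99999 at the design rates and about 0.95 with no difference. A positive value is therefore not evidence of benefit.

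**Step 4: where each limit crosses 0, with Arm B observed at 20%.** Solve (0.20 − pA) ± 1.645·√[(0.16 + pA(1 − pA))/n] = 0.

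| n per arm | SAP's upper bound below 0 | Lower bound above 0 |
|---|---|---|
| 111 | Arm A at about 29.5% or more | Arm A at about 12.0% or less |
| 140 | Arm A at about 28.4% or more | Arm A at about 12.8% or less |

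**Step 5: operating characteristics of the lower bound.** By exact binomial enumeration at 111 per arm, it exceeds 0 with probability 0.943 at 20% versus 6%, and 0.051 at 20% versus 20%. That is, to a close approximation, the one-sided 5% test for which the trial was sized.

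**The case against.** The strongest reply is that the bound is not the primary test. Protocol 9.6.1 compares the proportions by a normal approximation and offers the bound in addition. The SAP nowhere withdraws that test, and a log-rank p-value for A versus B is planned. If the point estimate is printed and the interval is symmetric, the lower limit follows: 2 × 0.14 − 0.213 = 0.067. All of this stands. It means that the hypothesis is not left untested and no data are lost. It does not make the listed limit right. SAP 4.2 gives nothing else for the primary endpoint, and the log-rank test is a different analysis that both documents place as secondary. Protocol 9.6.2 makes evaluations of secondary objectives two-sided. Reading that across to the log-rank test is reasonable, since time to CIN2+ is a listed secondary endpoint, but the protocol does not say so for this test.

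A second reply is that *proportion*, as used in SAP 4.2 and in the validation sentence of SAP 3, echoes the protocol and could mean CIN2+-free, so a programmer working from the protocol might produce the right limit. That is possible, but it is not the plain reading. SAP 3 places the bound on cumulative rates directly after defining the cumulative rate of CIN2+, and SAP 4.2 and 4.2.2 attach the phrase to subjects who developed the event. The CIN3+ wording does not settle the matter alone, because a two-sided interval is informative on either scale. If both readings remain open, a double-programmed primary result still needs one of them fixed.

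**Conclusion.** The concern holds. Followed literally, SAP 3 and 4.2 deliver a limit on the wrong side for a one-sided superiority question, and they contradict the scale in protocol 9.6.1. At the design rates the reported limit would be +0.213 instead of the informative +0.067, and it would be positive with or without a benefit. The sizes rest on a simple-proportion approximation at the design rates. The direction of the error does not depend on that approximation, on the estimator or on the amount of censoring. The defect lies in the limit that is specified and validated. The protocol's one-sided comparison still stands. It must be fixed before analysis because it concerns the only inferential output listed for the primary endpoint.

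**What to change.** In SAP 3 and 4.2, including both double-programming statements, do one of the following:

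- (a) Specify a one-sided 95% **lower** confidence bound for Arm B minus Arm A cumulative CIN2+ rates, with superiority of Arm A if the bound is above 0.
- (b) State that the upper bound applies to the CIN2+-free proportions, as in protocol 9.6.1, with superiority if the bound is below 0. This also requires replacing the reference to cumulative rates in SAP 3.

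In either case, list the protocol's one-sided 5% asymptotic-normal test and its p-value under the primary endpoint as the primary test, and keep the stratified log-rank as secondary. The text should also name the estimator and variance behind the test and the bound, because protocol 9.6.1 uses Turnbull with a generalized Greenwood variance and SAP 3 uses Kaplan-Meier.

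The cost is SAP wording and the matching change to the analysis program. Design, data, sample size and alpha are unaffected.

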(The following paragraph supersedes Clarification Memo [CM] #2, dated 01/02/1014.) Directed biopsies will be obtained from areas suspicious for CIN. ~~Biopsies are taken only if lesions are seen upon colposcopy.~~ In the event lesions are not seen upon colposcopy but the cytology specimens show presence of HSIL, then the participant should return to the study clinic for repeat colposcopy and other diagnostics procedures such as endocervical curettage (ECC), random cervical biopsies (**if not already done**), or diagnostic LEEP. Results of these diagnostic tests must be recorded on the appropriate CRF. ~~Slides from biopsies of CIN2+ and biopsies without CIN2+ will be submitted for review.~~ If CIN2+ is detected by biopsy, the participant will undergo LEEP.

- c. Sample Informed Consent, What do I have to do if I am in this Study?, Groups A and B: At the study visit about 6, 18, and 30 months after the entry visit you will also have a colposcopy and biopsies if any abnormal areas are seen. **At months 18 and 30, you will have two biopsies performed whether or not abnormal areas are seen.**

3. Additional clarifications were made to Section 6.3.10.

- a. The subsection, "Diagnoses," now reads:

Diagnoses

(Per CM #1, dated 02/05/1013.) After entry, record any new diagnoses made since the last visit using the ACTG criteria for clinical events and other diseases.

(Per CM #1, dated 02/05/1013.) Except for invasive cancer, cervical cytology and histology results do not need to be recorded as events; these results will be entered on study-specific CRFs only.

(New language) Record all histology results from procedures for the diagnosis or treatment of cervical HSIL (such as cervical conization or hysterectomy) and from biopsies performed related to the presence or absence of squamous intraepithelial lesions on the appropriate CRFs.

- b. The subsection, "LEEP," now reads:

(The following paragraph supersedes item 4b in LoA #2, dated 08/09/1012.)

LEEP

Participants found to have CIN2+ by biopsy at any point during the study will be offered LEEP **or other excisional treatment** (except for participants in Arm A **prior to week 26** who have CIN2+ on pre-cryotherapy biopsy at entry). If the participant had a prior LEEP, treatment of recurrent **or incompletely treated**

CIN2+ is at the discretion of the site investigator. These participants will continue on study.

(No changes to the remainder of this subsection.)

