#### 4.1.4 Treatment Status

Table with:

- listing of Arm A participants who did not have cryotherapy and reasons
- listing of Arm B participants who did not have LEEP after CIN2+ diagnosis
- listing of Arm B participants with abnormal cytology who do not have biopsies obtained at baseline

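### The latest amendment letter conflicts with itself on LEEP after an Arm A entry biopsy, and the SAP's per-protocol rule and listings would not show Arm A women excised before week 26

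*SAP*

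**What the plan says.** **Protocol, as amended.** Since Letter of Amendment #1, every Arm A woman has one or two biopsies immediately before cryotherapy and is told the result. The same letter states that CIN2 or CIN3 on those biopsies is not a primary endpoint.

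The latest letter of amendment (the one that follows the March 2015 DSMB review) revises section 6.3.10 in two places:

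- The paragraph on colposcopy and directed biopsies ends: "If CIN2+ is detected by biopsy, the participant will undergo LEEP". It has no exception by arm or by time.
- The LEEP paragraph excepts Arm A women, before week 26, "who have CIN2+ on pre-cryotherapy biopsy at entry".

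**Per-protocol analysis.** Protocol 9.6.1 limits it to "only the participants who adhere to the specified procedures in Arms A and B". SAP section 3 makes this concrete. For Arm A it asks only for "Arm A participants who had week 0 cryotherapy". For Arm B, one qualifying group is "women who had LEEP performed prior to week 16 after the week 0 CIN2+ on biopsy regardless of cytology result".

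**Reporting.** SAP 4.1.4 plans a "listing of Arm A participants who did not have cryotherapy and reasons" and a "listing of Arm B participants who did not have LEEP after CIN2+ diagnosis", plus a listing of Arm B women with abnormal cytology and no baseline biopsy. The note under SAP 4.2 adds: "LEEP outcome prior to week 16 will be considered baseline evaluation and will not be used as an endpoint". That note is not limited to one arm.

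**The concern.** The two sentences in the letter give different answers for one identifiable group: Arm A women with CIN2+ on the entry biopsy. A site that follows the first could perform LEEP shortly after cryotherapy. A site that follows the second would not. The same letter also allows diagnostic LEEP when cytology shows HSIL and no lesion is seen, without limiting this to an arm.

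Women with CIN2+ at entry are the ones in whom cryotherapy can most visibly fail at week 26. If LEEP removes the lesion first, the week 26 biopsy is likely to be clear. Under the SAP such a woman remains in the Arm A per-protocol set. Any residual disease in a LEEP specimen before week 16 is treated as baseline. The per-protocol comparison would then credit cryotherapy with some outcomes that LEEP produced, and a reader could not see how many.

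**Working it through.** **1. How the amendment texts fit together.**

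- Letter #2, item 4b, limited the biopsy sentence to CIN2+ found after entry and wrote the Arm A exception into the LEEP paragraph.
- Clarification Memo #2 restated the biopsy paragraph without the after-entry limit.
- The latest letter supersedes that memo's paragraph, again without the limit. It also states that its LEEP paragraph supersedes item 4b of Letter #2.
- Letter #2, item 4a (Schedule of Events), still carries the Arm A exception.

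The conflict is therefore between operative sentences, not between old and current text.

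**2. Whether any planned output would reveal an Arm A LEEP before week 26.**

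| Planned output | Identifies Arm A LEEP before week 26? |
|---|---|
| SAP 3, Arm A per-protocol rule | No: week 0 cryotherapy only |
| SAP 4.1.4 listings | No: missed cryotherapy (A); missed LEEP or biopsy (B) |
| SAP 4.2, baseline CIN2+ successfully treated before week 26 | No: one count is Arm B only, the other has no arm split |
| SAP 4.2.4, adverse events after LEEP | No: no arm split, no timing |
| SAP 4.2.1, curves for women with baseline CIN2+ | Contains these women, does not identify them |

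The rules also leave a gap in time. LEEP before week 16 is baseline and the week 26 window opens at week 20 (26 − 6), so weeks 16 to 20 are not addressed.

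**3. The protocol's own figures.** Protocol 9.4 assumes 24% CIN2+ at first colposcopy, 80% cytology sensitivity and 90% treatment efficacy: 0.24 × 0.80 × 0.90 = 17.3%, against the stated 17%. The sample size for 20% versus 6%, one-sided 5%, 90% power, with continuity correction, reproduces at 111 per arm. This point disputes neither figure.

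**4. Women under the conflicting text.** 0.24 × 140 = 33.6, about 34 Arm A women, or 0.24 × 111 = 26.6 of the 111 evaluable. This is the number exposed to the ambiguity, not the number who had LEEP.

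**5. Possible size of the bias.** Take p = 6% as the Arm A rate with cryotherapy alone (protocol 9.4). The following are assumptions, not figures for this group in the documents:

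- f, the fraction of entry-CIN2+ women who have LEEP before week 26: 10%, 25% or 50%;
- s, the share of cryotherapy failures that arise in entry-CIN2+ women: 50% to 100%;
- LEEP clears 90% of would-be failures (the efficacy that 9.4 states for Arm B treatment, borrowed here).

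Formulas for the observed Arm A rate:

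- kept (SAP rule): p(1 − 0.9sf)
- excluded: p(1 − sf) / (1 − 0.24f)
- counted as failures: p(1 − sf) + 0.24f

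Example with f = 0.5, s = 1: kept 0.06 × 0.55 = 3.3%; excluded 0.03 / 0.88 = 3.4%; failures 0.03 + 0.12 = 15.0%.

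| f | Kept | Excluded | Counted as failures |
|---|---|---|---|
| 10% | 5.5–5.7% | 5.5–5.8% | 7.8–8.1% |
| 25% | 4.6–5.3% | 4.8–5.6% | 10.5–11.3% |
| 50% | 3.3–4.6% | 3.4–5.1% | 15.0–16.5% |

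At f = 0 every column is 6%. Censoring at LEEP gives nearly the same estimate as exclusion, because events count only from the week 26 visit and women censored earlier have left the risk set.

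**The case against.** **The exception is the more specific text.** The biopsy sentence is general wording carried over from version 1.0. The Arm A exception is explicit in the same letter's LEEP paragraph and in the Letter #2 Schedule of Events change. Sites may well have followed the exception, and no passage reports or estimates any Arm A LEEP before week 26. This stands: the number of women affected may be zero, and the documents do not show that crossover happened. It does not remove the need to reconcile two operative sentences, and it does not cover diagnostic LEEP.

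**A reader might infer that about a quarter of Arm A failures are hidden.** If 30% of the 33.6 women had LEEP and cryotherapy would have failed in 20% of them, 33.6 × 0.3 × 0.2 = 2.0 events, or 24% of the planned 8.4 (0.06 × 140). The documents do not support this. Neither share appears in them. With 10% failure, the complement of the 90% efficacy in 9.4, the result halves to 1.0 event, or 12%. The 24% prevalence itself rests on month 6 colposcopy in the cited trial, not on entry biopsies.

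**A reader might infer that these women should be coded as failures.** Letter #1 says that entry CIN2 or CIN3 is not an endpoint. In Arm B, women with entry CIN2+ and LEEP before week 16 stay in the per-protocol set as non-failures, so the coding would be asymmetric. In the table above it also moves the rate further from 6% (to 7.8–16.5%) than keeping the women does (to 3.3–5.7%).

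**The analysis is secondary.** This also stands. The trial compares strategies, and the intent-to-treat primary analysis keeps these women by design.

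**Conclusion.** The point holds as a conflict between two operative amendment sentences, combined with a SAP that could not detect its consequences. The Arm A per-protocol rule is looser than the definition in protocol 9.6.1, and no planned output identifies Arm A women excised before week 26.

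Any such women would bias the secondary per-protocol comparison towards Arm A, provided that LEEP clears some lesions that cryotherapy would have left. The size is unknown. About 34 of 140 women fall under the conflicting text if the protocol's 24% applies to Arm A entry biopsies. If 10% to 50% of the exposed women had LEEP, a cryotherapy-only rate of 6% would be observed as 5.7% down to 3.3%; with no crossover there is no bias. A reader might extend the point to the primary result, but the documents do not support that.

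**What to change.** 1. **Reconcile the two paragraphs of revised section 6.3.10** in the latest letter, together with the Schedule of Events, on LEEP after CIN2+ on the Arm A entry biopsy. Which rule applies is for the protocol team.
2. **Align SAP section 3 with protocol 9.6.1.** Treat LEEP or other excision before the week 26 visit as a departure from Arm A procedures. If the team decides in step 1 that LEEP is a specified step for some of these women, the SAP should say so; the listing and displays below are needed either way.
3. **Add to SAP 4.1.4** the number and a listing of Arm A women with excision before the week 26 visit, giving timing, indication, entry histology and LEEP histology.
4. **Show the per-protocol result** with these women kept, with them excluded or censored at LEEP, and, as an upper bound only, counted as failures. Failure coding should not be the sole per-protocol rule.

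**Cost.** A wording change, one listing and a few secondary runs. The latest letter already requires histology from diagnostic and treatment procedures on the CRF. The limitation to state is that exclusion alone does not remove the bias, because it drops high-risk women from Arm A only (3.4–5.1% at 50% LEEP, close to 3.3–4.6% when kept). The intent-to-treat primary analysis does not change.
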